4.3. Secondary Estimands Analyses

4.3.1. Secondary endpoint(s)

Estimands for the secondary variables will use the same inhaler comparison, population and strategy for the intercurrent event as for the primary estimand (see section 1.1.2). This means the estimated treatment effect comparing the ELLIPTA inhaler to the BREEZHALER inhaler will be based on the stratum of participants who were able to attempt demonstration on both inhalers (S₀₀). All comparisons will be made at the two-sided 5% significance level.

4.3.1.1. Definition of endpoint(s)

The secondary endpoints for analysis are:

- Participants who still make at least one critical error after receiving further instruction (up to 3) from the HCP.
- Participants who make at least one overall error after reading the PIL(s).
- Participants who still make at least one overall error after receiving further instruction (up to 3) from the HCP.
- The amount of time taken to demonstrate inhaler use without HCP intervention (T1).
- The amount of time taken to be given instruction by the HCP (up to 3 times) on use of the inhaler and to demonstrate inhaler use (T2).
- The total amount of time taken to demonstrate correct inhaler use (T1+T2).
- Requiring further instruction from the HCP to demonstrate correct inhaler use.
- Ease-of-use from ease-of-use questionnaire (easy or difficult).
- Willingness to continue with the inhaler using a visual analogue scale (VAS) between 0 ~~CCI~~ to 100 ~~CCI~~
- Inhaler preference from questionnaire (ELLIPTA, BREEZHALER or no preference).

4.3.1.2. Critical error after reading the PIL(s)

Participants may receive further instruction (maximum of 3) if any error was made after reading the PIL. For the endpoint of participants who still make at least one critical error after receiving further instruction (up to 3) from the HCP:

- a) The variable for attempt 2 is participants making at least one critical error after receiving the first instruction from the HCP (attempt 2). The denominator will include all participants who fall in the S₀₀ stratum. Participants who do not receive the first HCP instruction are assumed to have zero critical errors.
- b) The variable for attempt 3 is participants making at least one critical error after receiving the second instruction from the HCP (attempt 3). The denominator will include all participants who fall in the S₀₀ stratum. Participants who do not receive the second HCP instruction are assumed to have zero critical errors.
- c) The variable for attempt 4 is participants making at least one critical error after receiving the third instruction from the HCP (attempt 4). The denominator will include all participants who fall in the S₀₀ stratum. Participants who do not receive the third HCP instruction are assumed to have zero critical errors.

The population-summary measure for a)-c) is the odds ratio of participants making at least one critical error between the ELLIPTA and BREEZHALER inhalers. The analysis method will be the same as for the primary endpoint.

Note: This model will only be fitted if there is sufficient data, otherwise summary statistics will be presented.

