9.4.2. Secondary Endpoint(s)

Estimands for the secondary variables will use the same inhaler comparison, population and strategy for the intercurrent event as for the primary estimand. This means the estimated treatment effect comparing the ELLIPTA inhaler to the BREEZHALER inhaler will be based on the stratum of participants who were able to attempt demonstration on both inhalers. All comparisons will be made at the two-sided 5% significance level.

Objectives	Statistical analysis methods
To compare the proportion of participants who still make at least one critical error after	
Participants who still make at least one critical error after receiving further instruction (up to 3) from the HCP.
 
Participants receive further instruction if an error was made after reading the PIL.

Objectives	Statistical analysis methods

receiving further instruction from the Healthcare Professional (HCP) for ELLIPTA and BREEZHALER inhalers
	
 • Variable: participants making at least one critical error after the a) first instruction from the HCP (attempt 2), b) the second instruction from HCP (attempt 3) and c) third instruction from the HCP (attempt 4). • Population-summary measure: The odds ratio of participants making at least one critical error between the ELLIPTA and BREEZHALER inhalers. 
a) The denominator will include all participants who fall in the S₀₀ stratum. Participants who do not receive the first HCP instruction are assumed to have zero critical errors.
 
b) The denominator for those that require a second further instruction will include all participants who fall in the S₀₀ stratum. Participants who do not receive the second HCP instruction are assumed to have zero critical errors.
 
c) The denominator for those that require a third further instruction will include all participants who fall in the S₀₀ stratum. Participants who do not receive the third HCP instruction are assumed to have zero critical errors.
 
The analysis method will be the same as for the primary endpoint.
 
Note: This model will only be fitted if there is sufficient data, otherwise summary statistics will be presented.

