Design Features	
 This is a randomized, multi-centre, open label, placebo inhaler-handling study with a 2x2 complete block crossover design to study critical errors, overall errors, training/teaching time, ease-of-use and willingness to continue and preference attributes of two dry powder inhalers: ELLIPTA and BREEZHALER. Each participant will be randomized to one of the four groups: ELLIPTA followed by BREEZHALER or BREEZHALER followed by ELLIPTA and further refined by assignment of the preference questionnaire version (i.e. version 1 or 2). The study involves two visits which can be completed on the same day. Visit 1 may be completed up to 30 days after visit 0. A participant is considered to have completed study treatment if demonstration of both inhalers has been completed on Day 1 (Visit 1). A participant is considered to have completed the study if all assessments have been completed on Day 1 (Visit 1). Period 1 is complete once demonstration has been completed on the first inhaler after reading the PIL (or receiving up to 3 further HCP instructions), after completing the "Ease of Use" questionnaire and after completing the "Willingness to Continue" question. Period 2 is complete once demonstration has been completed on the second inhaler after reading the PIL (or receiving up to 3 further HCP instructions), after completing the "Ease of Use" questionnaire and after completing the "Willingness to Continue" question. Participants may take up to a 30-minute break between period 1 and period 2. 				

Overview of Study Design and Key Features	
	
 Participants may take up to a 30-minute break after period 2 prior to completion of the preference questionnaire. A participant may withdraw from the study at any time at his/her own request or may be withdrawn at any time at the discretion of the investigator for safety, behavioural, or compliance reasons.

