3. ANALYSIS SETS

Analysis Set	Definition / Criteria	Analyses Evaluated
Screened	
 • All participants who were screened for eligibility and signed the ICF. 	
 • Screening status and reasons for screen failures
Enrolled	
 • All participants enrolled and for whom a record exists on the study database. 	
 • Study population
Randomised	
 • All participants who were randomly assigned to study intervention in the study. • Any participant who receives a randomisation number will be considered to have been randomised. 	
 • Study population
Full Analysis Set (FAS)	
 • All randomised participants who used at least one study inhaler. • Data will be reported according to the randomised study intervention. 	
 • Study population • Safety
Safety	
 • All randomised participants who used at least one study inhaler. • Data will be reported according to the study intervention actually received. 	
 • Safety
Modified intention-to-treat (mITT)	
 • All participants who were randomised to study intervention in the study, completed reading of the PIL and attempted demonstration of both inhalers. • Data will be reported according to the randomised study intervention. 	
 • Efficacy

For CDISC purposes, the modified intention-to-treat (mITT) analysis set refers to the performance evaluable analysis set as defined within the protocol.

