4.3.1.3. Overall errors

For the endpoint of participants who make at least one overall error after reading the PIL (attempt 1), the population-summary measure will be the odds ratio between the ELLIPTA and BREEZHALER inhalers. The analysis method will be the same as for the primary endpoint.

The population-summary measure and analysis method defined above for participants who make at least one overall error after reading the PIL will be performed for the endpoint of participants who still make at least one overall error after receiving further instruction (up to 3) from the HCP. Participants may receive up to three further instructions if any error was made after reading the PIL.

- a) For participants who make at least one overall error after receiving the first instruction from the HCP (attempt 2), the denominator will include all participants who fall in the S₀₀ stratum. Participants who do not receive the first instruction by the HCP are assumed to have zero overall errors.
- b) For participants who make at least one overall error after the second instruction from the HCP (attempt 3), the denominator for those that require a second further instruction will include all participants who fall in the S₀₀ stratum. Participants who do not receive the second HCP instruction are assumed to have zero overall errors.
- c) For participants who make at least one overall error after the third instruction from the HCP (attempt 4), the denominator for those that require a third further instruction will include all participants who fall in the S₀₀ stratum. Participants who do not receive the third HCP instruction are assumed to have zero overall errors.

Note: the model will only be fitted where further instruction is required provided there is sufficient data, otherwise summary statistics will be presented.

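### Post-instruction error endpoints give a zero score for not receiving instruction rather than for correct use, so a participant who failed and then stopped can count as error-free (minor)

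*SAP*

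**What the plan says.** SAP 4.3.1.2 defines three critical-error variables, one each for Attempts 2, 3 and 4. For each, "The denominator will include all participants who fall in the S₀₀ stratum". The scoring rule for Attempt 2 is "Participants who do not receive the first HCP instruction are assumed to have zero critical errors". Attempts 3 and 4 have the same rule: "Participants who do not receive the second HCP instruction are assumed to have zero critical errors" and "Participants who do not receive the third HCP instruction are assumed to have zero critical errors". SAP 4.3.1.3 repeats it for overall errors, starting with "Participants who do not receive the first instruction by the HCP are assumed to have zero overall errors". Protocol 9.4.2 contains the same rules, so six comparisons are affected.

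The efficacy set (mITT, SAP 3) is "All participants who were randomised to study intervention in the study, completed reading of the PIL and attempted demonstration of both inhalers". It does not require the instruction sequence to be finished. On leaving the study, SAP 1.2 says "A participant may withdraw from the study at any time at his/her own request".

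On who is instructed, Protocol 9.4.2 says "Participants receive further instruction if an error was made after reading the PIL". SAP 4.3.1.2 and 4.3.1.3 are weaker and say only that such participants may be instructed.

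Two neighbouring rules use a different condition. SAP 4.3.1.4 classifies participants by whether they require instruction. SAP 4.3.1.5 gives a T2 of zero minutes only to those who used the inhaler correctly after reading the leaflet and so needed no instruction.

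**The concern.** The zero score stands in for an attempt that was never made. That is sound when the attempt was unnecessary because the participant had already used the inhaler correctly. It is unsound when the participant had just failed and no further instruction followed. The rule does not separate the two, because it depends on whether instruction was received and not on why it was not.

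The second kind of participant would enter the post-instruction odds ratios as a success at every later attempt. SAP 4.3.1.4 would still count the same person as requiring instruction. If the failure was at Attempt 1, SAP 4.3.1.5 would also censor them for T1. These endpoints are likely to have few discordant pairs, so a handful of wrong scores could change an odds ratio and its p-value.

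**Working it through.** **The plan's own figure.** The plan gives no figure for these secondary endpoints. Its sample size, for the primary endpoint, reproduces from SAP 5 (odds ratio 0.3, SD 2.785 on the log scale, two-sided 5%, 90% power):

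n per sequence = (1.960 + 1.282)² × 2.785² / (ln 0.3)² = 10.507 × 7.756 / 1.450 = 56.2, rounded up to 57; 2 × 57 = 114.

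The primary endpoint is Attempt 1, before any instruction, so the scoring rule affects neither it nor N.

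**Who is affected.** Take a participant with an error at the last observed attempt on an inhaler and no further instruction on it.

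- Left during the first inhaler, before trying the second: outside S00 and mITT, so excluded and not scored.
- Stopped on the first inhaler after a failed attempt but went on to try the second: in S00, and scored zero at later attempts on the first.
- Stopped partway through the second inhaler after a failed attempt: in S00, and scored zero at later attempts on the second.
- Failed with non-critical errors only: a zero for critical errors agrees with what was last seen; only the zero for overall errors is doubtful.
- Received an instruction but left before the next attempt: no rule covers that attempt. After the first instruction, for example, Attempt 2 has no rule, while Attempts 3 and 4 are scored zero because the second and third instructions were not received.

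**Size, on assumed counts.** The documents give no expected discordant counts after instruction, so the counts below are assumptions. Let b be the number of participants with an error on ELLIPTA only and c the number on BREEZHALER only. The odds ratio is b/c, and the exact two-sided McNemar p is 2 × P(X ≤ min(b, c)) for X ~ Binomial(b + c, 0.5). The planned model also has a period term, ignored here.

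For 2:10, p = 2 × (1 + 12 + 66) / 4096 = 0.039. Suppose one participant scored zero on both inhalers was in truth an uninstructed ELLIPTA failure. Counting that error gives 3:10, and p = 2 × (1 + 13 + 78 + 286) / 8192 = 0.092.

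| Split under the SAP rule | OR, p | One ELLIPTA failure counted | One BREEZHALER failure counted |
|---|---|---|---|
| 1:8 | 0.125, 0.039 | 2:8, 0.25, 0.109 | 1:9, 0.111, 0.0215 |
| 2:10 | 0.20, 0.039 | 3:10, 0.30, 0.092 | 2:11, 0.182, 0.0225 |
| 3:12 | 0.25, 0.035 | 4:12, 0.333, 0.077 | 3:13, 0.231, 0.0213 |

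If the ELLIPTA failure belongs to someone who also had a BREEZHALER error at that attempt, the pair becomes concordant instead. Then 2:10 becomes 2:9 and p = 2 × (1 + 11 + 55) / 2048 = 0.065. With no such participants, nothing changes.

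**Direction.** The rule favours whichever inhaler has more uninstructed failures. SAP 5 assumes 6% ELLIPTA-only and 20% BREEZHALER-only critical errors. If that pattern carries over, BREEZHALER would more often be favoured, and the rule would usually shrink the ELLIPTA advantage.

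**The case against.** The strongest reply is that under the protocol, not receiving instruction means not needing it. Protocol 4.1, 6.4 and 8.1.1 all send a participant with any error to another instruction, up to three. Declining instruction while staying in the study is not foreseen: Protocol 7.1 treats stopping the intervention as withdrawal. Assessment takes place on one day, and SAP 5 expects no withdrawals. The intended reading is therefore clear and the case rare. The post-instruction models are also fitted only if data are sufficient. This stands, and it is why the point is minor. It does not remove the point: the rule as written gives the wrong score whenever the case arises, and neither document says how a failed attempt with no later attempt is scored.

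Three stronger readings are tempting but not supported.

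- A reader might infer that everyone who fails and withdraws is counted as a success. Those who leave before trying the second inhaler are outside S00 and mITT.
- A reader might infer that the same person is a censored failure for T2, so that the SAP contradicts itself. SAP 4.3.1.5 censors T2 failures after the fourth attempt, and SAP 4.1.2.1 ends T2 there for those who never succeed. Someone who stops earlier has no T2 rule, which is a gap and not a contradiction. The tension that can be shown is with the instruction endpoint and, after a failure at Attempt 1, with T1.
- A reader might infer that the rule tilts the comparison towards ELLIPTA. The direction is not fixed, and the plan's own rates point the other way.

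**Conclusion.** The point holds as a minor one. The scoring rule in SAP 4.3.1.2 and 4.3.1.3 and Protocol 9.4.2 uses the wrong condition, and in six secondary comparisons it can score as error-free an S00 participant whose last attempt had an error of the type analysed.

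The expected effect is close to nil because the plan expects no withdrawals. The illustration shows only that one case could move a secondary result across 5% when discordant pairs are few; it rests on assumed counts and on a test without the period term. That the rule would more often favour BREEZHALER rests on the 6% and 20% rates, set for Attempt 1, also holding for participants who stop early.

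**What to change.** In SAP 4.3.1.2 and 4.3.1.3, replace the condition of not receiving an instruction with not requiring it because a previous attempt was error-free. Protocol 9.4.2 has the same wording; record the change in SAP 4.7.

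Add one rule for everyone else. A participant whose last observed attempt had an error and who has no later attempt, whether or not instruction was given, keeps that attempt's status at the later attempts. Apply it separately for critical and overall errors, so that a last attempt with only non-critical errors stays at zero for critical errors. This also covers the participant who was instructed but left before trying again.

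Add a sensitivity analysis that treats those later attempts as missing. It is needed because carrying the status forward assumes no benefit from instruction that was not given or not tested, which the data cannot check.

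The cost is SAP wording, one programming condition and the sensitivity run, all before database lock. If no such participant occurs, the results are unchanged.

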4.3.1.3. Overall errors

For the endpoint of participants who make at least one overall error after reading the PIL (attempt 1), the population-summary measure will be the odds ratio between the ELLIPTA and BREEZHALER inhalers. The analysis method will be the same as for the primary endpoint.

The population-summary measure and analysis method defined above for participants who make at least one overall error after reading the PIL will be performed for the endpoint of participants who still make at least one overall error after receiving further instruction (up to 3) from the HCP. Participants may receive up to three further instructions if any error was made after reading the PIL.

- a) For participants who make at least one overall error after receiving the first instruction from the HCP (attempt 2), the denominator will include all participants who fall in the S₀₀ stratum. Participants who do not receive the first instruction by the HCP are assumed to have zero overall errors.
- b) For participants who make at least one overall error after the second instruction from the HCP (attempt 3), the denominator for those that require a second further instruction will include all participants who fall in the S₀₀ stratum. Participants who do not receive the second HCP instruction are assumed to have zero overall errors.
- c) For participants who make at least one overall error after the third instruction from the HCP (attempt 4), the denominator for those that require a third further instruction will include all participants who fall in the S₀₀ stratum. Participants who do not receive the third HCP instruction are assumed to have zero overall errors.

Note: the model will only be fitted where further instruction is required provided there is sufficient data, otherwise summary statistics will be presented.

4.3.1.4. Requiring further instruction

For the endpoint of requiring further instruction from the HCP to demonstrate correct inhaler use, the variable is participants who do or do not require further instruction from the HCP. Participants who require ≥ 1 instructions from the HCP (maximum of 3) will be considered as requiring further instruction. The population-summary measure is the number and percentage of participants who do or do not require further instruction from the HCP. To compare the proportion of requiring further instruction on the ELLIPTA inhaler vs. requiring further instruction on the BREEZHALER inhaler, a McNemar's test will be performed.

4.3.1.5. Training/teaching time

The population-summary measure for teaching/training time is the median time to demonstrate inhaler use. The median time will be taken from the Kaplan-Meier model. Additionally, the

mean (SD), median, minimum and maximum will also be presented for participants who demonstrate correct inhaler use.

- a) T1: the amount of time taken to correctly demonstrate inhaler use without HCP intervention. Participants who fail to demonstrate the correct use will be censored at the end of T1, having completed demonstration of the first attempt.
- b) T2: the amount of time taken to be given instruction by the HCP (up to 3 times) on use of the inhaler and to demonstrate inhaler use. Participants who demonstrate correct use after reading the PIL (and therefore do not require further instruction) will be considered as demonstrating correct use at T2 and time taken to demonstrate correct use will equal to 0 minutes. Participants who fail to demonstrate the correct use will be censored at the end of T2, after completing the fourth attempt.
- c) The total amount of time taken to demonstrate correct inhaler use until correct demonstration is observed is calculated by: T1+T2. Kaplan-Meier survivor functions of T1+T2 will be obtained for each inhaler group and plotted on the same figure.

